5.1.3 Other study parameters

- Baseline characteristics including:
 - Demographics, i.e. age, gender, BMI, smoking status, American Society of Anesthesiologists class (ASA).
 - Comorbidities, including history of the following diseases: myocardial infarction, cerebrovascular disease, congestive heart failure and cancer. Currently diagnosed with: diabetes, coronary artery disease, chronic renal failure, cancer, chronic obstructive pulmonary disease, peripheral vascular disease, and hypertension.
 - Medication use, including beta blockers, angiotensin converting enzyme inhibitors, calcium blockers, diuretics, statins, insulin, oral antidiabetics.
 - Surgical history, including coronary revascularization, pacemaker or implantable cardioverter defibrillator (ICD).
 - Laboratory results of preoperatively measured blood biomarkers, i.e. hsTroponin, C-reactive protein (CRP), brain natriuretic peptide (BNP), hemoglobin (Hb) and creatinine in blood. Imaging biomarkers are electrocardiogram (ECG) and transthoracic echocardiogram (TTE).
 - Referral of the screening anesthesiologist at the preanesthesia consultation clinic to a cardiologist or other specialist before surgery
 - Preoperative WHODAS 2.0
- Intraoperative:
 - Anesthesia related including type of anesthesia (general or spinal), vital signs (i.e. blood pressure, heart rate, eCO2).

- Surgical related factors: surgical risk, surgical specialty, blood loss, number of blood transfusions and fluid balance.
- Postoperative:
 - Troponin I monitoring at postoperative day 1-3 as being part of routine care.
 - Laboratory results of postoperative measured blood biomarkers, i.e. hsTroponin, CRP, BNP, Hb and creatinine in blood on postoperative day 1-3. Imaging biomarkers (ECG and TTE) on postoperative day 2.
 - Rehospitalization within 6 months after surgery.

5.2 Randomization, blinding and treatment allocation

Not applicable

5.3 Study procedures

Patient recruitment and preoperative clinical practice

Study eligibility will be checked by study personnel working at the preanesthesia outpatient clinic. Patients will be approached during the preoperative consultation and will be informed about the proposed study. Patients will receive extra study information together with the WHODAS 2.0 questionnaire, in case they are interested in participation in this study. Patients will be approached by telephone one week before surgery and asked if they would like to participate on this study. Hence, patients have the time between the preanesthesia visit and one week before surgery, which is more than 24 hours, to decide if they are willing to participate. If the patient is interested in participation, the WHODAS 2.0 survey will be taken by the researcher during this telephone call and patients will be assigned a study number. This number is used as a reference for storage of study data in the Case Report File (CRF). Access to study numbers correlating to patient names will only be available to the principal study investigator, research personnel involved in including patients and study monitors/auditors. Informed consent will be signed at hospital admission before surgery. If patients decline study participation, they will receive perioperative care as usual. Study material collected before signing informed consent (e.g. WHODAS 2.0 survey) will be deleted for patients who were interested during the telephone call but rejected participation at the moment of signing informed consent.

All patients are required to visit the preanesthesia outpatient clinic for preoperative consultation as part of usual care (i.e. non-study related). The following procedures will be performed:

- Patient characteristics regarding demographics, comorbidities, medication use, surgical and anesthetic factors will be collected by the anesthesiologist.

- If requested by the screening anesthesiologist, venous blood will be sampled for additional diagnostic testing as part of routine care. Data regarding information about preoperative biomarker determination will be collected. This means that not all patients require preoperative venous sampling, only if indicated.
- An ECG will be performed and assessed by the screening anesthesiologist.

All data collected at the preoperative consultation clinic, including biomarker determination (i.e. ECG and blood biomarkers) will be interpreted as baseline measurements.

Hospital admittance and intraoperative data collection

For patients who agreed on study participation during the telephone call one week before surgery, informed consent will be signed by the patient and study investigator. If a patient decides to decline study participation at this point, this patient will receive routine care as usual. The treating anesthesiologist will be informed about participation and 7 cc blood will be drawn at the operation theatre immediately before induction of anesthesia. Blood will be collected, processed and stored at the Centrale Biobank (CBB) with corresponding study number. Blood biomarkers will be considered preoperative baseline values. During surgery, the following data will be collected:

- Vital signs, i.e. blood pressure, heart rate and ET-CO₂.
- Blood loss and number of blood transfusions
- Duration of surgery

Collection of intraoperative data is part of routine clinical care; no study related procedures will be conducted.

Postoperative in hospital stay

At postoperative day 1-3, the following procedures will be performed:

- Extra blood (7 cc each time) will be drawn during the standard blood sampling rounds in the morning. Blood will be processed and stored at the CBB.
- At postoperative day 2, an ECG and TTE will be performed by certified study personnel and uploaded at the local electronic health record (EHR) and a digital databank.
- In-hospital MAPE, such as MACE, unplanned ICU admission, respiratory disorders, renal failure, sepsis and/or SIRS and mortality will be monitored.

At the UMCU, troponin-I is routinely monitored in all patients, aged ≥ 60 years, undergoing major noncardiac surgery. In case troponin-I is elevated, routine (i.e. non-study related) hospital protocol procedures involve an ECG and consultation by an anesthesiologist. The anesthesiologist could consult a cardiologist for further examination. Additional diagnostic tests or initiation of therapy is

based on the cardiologist's discretion which is done in deliberation with the treating physician. Patients without troponin elevation only undergo cardiac assessment if deemed necessary by the ward physician. The treating physician will be blinded from the extra study related biomarker values except they request determination of (one or more) biomarkers as being part of usual care. The imaging biomarkers (i.e. ECG and TTE) will be uploaded in the EHR and on a digital databank. Due to logistical reasons, blinding of the imaging results is hardly feasible as all these results are uploaded to our local EHR automatically. By nature of the procedure, it might happen that an unexpected finding which could compromise the patient's health will be observed by the study personnel performing the ECG or TTE. In that occasion, the treating physician will be notified and the treatment strategy will be adapted if deemed necessary.

Hospital discharge of last patient

All blood samples stored at the CBB will be analyzed for the previous mentioned biomarkers in one batch after hospital discharge of the last patient, meaning that this information will not be available to the treating physician. High sensitive troponin will be determined in addition to the routinely measured troponin I as recent studies concluded that the detection rate of myocardial infarction is increased by factor 2 when using the high sensitive troponin compared to the contemporary assay²⁹. Only if the physician requested determination of (one or more) biomarkers as part of clinical care, the biomarker value is known as being part of routine clinical practice. Availability of these biomarkers to the treating physician will also be registered as these biomarkers could influence clinical care of these patients, and hence patient outcomes. Imaging biomarkers, i.e. ECG and TTE, will be assessed by an independent cardiologist who was unaware of any patient related clinical factors. All preoperative patient data will be merged to the biomarker results using the corresponding study number and hospital identifier.

6 month follow up

Patients will be followed up for 6 months after the day of surgery. Follow-up involves:

- Answering the WHODAS 2.0 questionnaire and a questionnaire regarding patient's health since the surgery (see F1. Vragenlijst 6 maanden follow up and F1. Vragenlijst WHODAS). Both questionnaires will be sent to the patient's home address and in the accompanying letter, a date with time will be mentioned during which patients could expect a telephone call by the researcher. The questionnaires will be taken off by telephone. In case of nonresponse, the researcher will approach the patient at another time to keep the response rate as high as possible.

- Approaching the patient's general practitioner to obtain information regarding postoperative events in the previous 6 months after surgery. This information will include clinically relevant events, such as MACE, hospital admission/consultation and change in medication prescription. In case patients are admitted or consulted at a hospital, the corresponding treating physician will be approached as well for clinically relevant information.

Before sending the questionnaires to the patient's home address, the GBA (Gemeentelijke Basisadministratie) will be used to find out whether the patient is still alive, to avoid sending questionnaires and calling patients who have deceased. Follow up will end after completion of both questionnaires. All results will be merged to the preoperative patient characteristics and biomarker data using the corresponding study number and hospital identifier.

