4.3 Exclusion criteria

A potential subject who meets any of the following criteria will be excluded from participation in this study:

- Patients unable to fully comply to study needs (e.g. legally incapable patients or patients unable to communicate in Dutch or English).
- Patients with an American Society of Anesthesiologists (ASA) Physical status 5

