5. METHODS

5.1 Study parameters/endpoints

5.1.1 Main study parameter/endpoint

Disability is expressed by the WHODAS 2.0, which is based on difficulties experienced by the respondent in different functional domains including, cognition, mobility, self-care, getting along, life activities and participation during the previous 30 days. Disability is defined as a decrement in each functioning domain corresponding to score between 0% and 100%, in which no disability stands for a score of 0% and full disability represents a score of 100%, including death. The WHODAS 2.0 is easy to use and patient centered (see F1 for the questionnaire). In a validation study including noncardiac surgical patients, the WHODAS 2.0 has been found to be a clinically acceptable, valid, reliable and responsive instrument for measuring postoperative disability²⁷.

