8.3 Benefits and risks assessment, group relatedness

This is a non-therapeutic study without involvement of minors and/or incapacitated adults studying the independent prognostic effect of different PMI phenotypes and noncardiac MAPE on postoperative disability status. The burden to patients is low as in addition to routine care, only noninvasive imaging techniques (i.e. TTE and ECG) will be performed, extra venous blood will be drawn during standard blood sampling rounds, and a short questionnaire needs to be filled out twice. The study is associated with a negligible risk as appearance of any adverse events due to the study is very low. The patient might benefit from participation in this study as unexpected findings from the TTE and/or ECG might change the treatment strategy and individual prognosis of that patient.

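### A survivor who can no longer answer at 6 months has no route to a measured WHODAS 2.0 score, so severe disability among survivors is likely to be understated

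*Combined protocol and SAP*

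**What the plan says.** Section 5.1.1 makes WHODAS 2.0 disability the main endpoint. It describes the instrument as "based on difficulties experienced by the respondent in different functional domains", and fixes the ends of the scale so that "no disability stands for a score of 0% and full disability represents a score of 100%, including death". Death therefore has an assigned value.

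Section 5.3 (6-month follow-up) posts the form to the patient and then collects it by phone, with one remedy for a failed contact: "The questionnaires will be taken off by telephone. In case of nonresponse, the researcher will approach the patient at another time". The general practitioner is also approached, and treating hospital physicians where relevant, but for events rather than function: "This information will include clinically relevant events, such as MACE, hospital admission/consultation and change in medication prescription".

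Incapacity appears in two other places. Section 4.3 excludes at entry "Patients unable to fully comply to study needs (e.g. legally incapable patients or patients unable to communicate in Dutch or English". Section 8.3 states: "This is a non-therapeutic study without involvement of minors and/or incapacitated adults". Neither says what happens when a patient who was capable at consent loses capacity or speech afterwards.

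Section 7.1 expects 20% dropout at 6 months, plans multiple imputation for missing data without naming the imputation variables, and compares responders with non-responders on baseline characteristics.

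**The concern.** The route to a score is open at both ends of the scale and closed near the top. Mildly affected patients answer the call, and the dead receive 100%. A survivor too impaired to take part in an interview has no measured value, and calling again does not help. The study itself records events that can leave a patient in this state. Section 5.1.2 lists stroke and cardiac arrest under MACE, and sepsis, respiratory failure and unplanned ICU admission under noncardiac MAPE. Noncardiac MAPE is one of the exposures compared in the primary objective, and section 1 links PMI to sepsis and to respiratory and renal failure.

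Whether the score is missing then depends on the score itself. The dropout check would not reveal this, because it looks only at baseline and the incapacity arises after surgery. Disability-free survival is exposed in the same way: such a patient would very probably fail the 25% criterion, but the value would have to be imputed.

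**Working it through.** **Is there another route to a score?** Setting the sections side by side:

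| Patient at 6 months | Source of WHODAS 2.0 | Section |
|---|---|---|
| Alive, able to answer | Telephone interview | 5.3 |
| Alive, misses the call | Further approach to the same patient | 5.3 |
| Dead | Assigned 100% | 5.1.1 |
| Alive, unable to answer | None stated; imputation only | 5.3, 7.1 |

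**Illustration of size.** The plan states no figure on this point, so there is none to reproduce.

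Inputs from section 4.4:
- Mean WHODAS of 29 with and 15 without troponin elevation, a difference of 14.
- 11.0% incidence and about 1,000 patients over both centres. This gives 0.11 × 1,000 = 110 PMI and 890 non-PMI patients before dropout. (The section's own sample-size count is 104 with elevation.)

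Assumptions, none of them in the documents:
- 29 and 15 are true means.
- Patients who lose the ability to answer have a true score s = 75.
- They number k = 3, 5 or 8 in the PMI group (2.7%, 4.5%, 7.3%) and 1% of the non-PMI group (about 9 patients).
- Imputation gives them the mean of the remaining patients in their group.

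PMI mean without the lost patients = (29 × 110 − k × 75) / (110 − k):
- k = 3: 2,965 / 107 = 27.71, a fall of 1.29
- k = 5: 2,815 / 105 = 26.81, a fall of 2.19
- k = 8: 2,590 / 102 = 25.39, a fall of 3.61

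Non-PMI mean without the lost 1% = (15 − 0.01 × 75) / 0.99 = 14.39, a fall of 0.61.

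Net loss from the 14-point difference:
- k = 3: 1.29 − 0.61 = 0.68 (5%)
- k = 5: 2.19 − 0.61 = 1.58 (11%)
- k = 8: 3.61 − 0.61 = 3.00 (21%)

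Range over s, for k = 5:
- s = 60: 5 × 31 / 105 − 0.01 × 45 / 0.99 = 1.48 − 0.45 = 1.02 points (7%)
- s = 90: 5 × 61 / 105 − 0.01 × 75 / 0.99 = 2.90 − 0.76 = 2.15 points (15%)

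**Direction.** If a fraction f of a group with mean m is lost, the group mean falls by f / (1 − f) × (s − m). With s = 75, s − m is 46 for PMI and 60 for non-PMI. The difference shrinks only if the odds of loss with PMI exceed 60 / 46 = 1.30 times the odds without PMI. At equal proportions it widens. With 4.5% (5 of 110) lost in both groups, the PMI mean falls by 2.19 and the non-PMI mean by 5 / 105 × 60 = 2.86, so the difference grows by 0.67 points.

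**The case against.** **Missing scores will be multiply imputed, and the study holds useful predictors.** It has the preoperative WHODAS, comorbidities, in-hospital events, and general-practitioner and hospital information at 6 months. Deaths at 100% also supply high values in the same event groups. This stands in part. Filling in at the group mean is a simplification, and a good imputation model could recover some of the loss. But section 7.1 does not name the variables, and even a model with postoperative events would draw its living donors from patients with the same event who were well enough to answer.

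**The pilot means probably already carry similar nonresponse.** About 20% of pilot patients did not complete the 6-month WHODAS, so 29 may be a responder mean. Then 5 lost patients at 75 would put the true PMI mean at (105 × 29 + 5 × 75) / 110 = 31.1, and the observed difference would stay near the planned 14. This stands: the illustration does not show that the sample-size basis is wrong.

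**A reader might infer that sections 4.3 and 8.3 make a site close an incapacitated patient as lost.** The documents do not support that. Section 4.3 governs potential subjects at entry, and section 8.3 is part of the benefit-risk assessment. Section 5.4 gives only the subject's own wish or urgent medical reasons as grounds for withdrawal.

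**The gap may be narrower in practice.** Many survivors of these events can still answer. The form reaches the home before the call, and nothing forbids a carer from helping. The F1 questionnaires are not in the documents, so a proxy version there cannot be excluded. Stroke and cardiac arrest are MACE components, not themselves exposures in the primary objective. Follow-up procedures at the Toronto centre are not described. All this limits the size, but does not supply a rule.

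**Conclusion.** The point holds as a gap in data collection. As written, a living patient who cannot answer has no measured primary outcome, and the planned imputation and baseline dropout check are unlikely to repair or reveal this. Severe disability among survivors is therefore likely to be understated.

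The effect on the comparisons is conditional. Bias towards no effect, for disability and for disability-free survival, requires clearly more frequent loss with PMI or noncardiac MAPE than without. That is plausible, given the events involved, but not documented. A reader might infer that attenuation is certain, or take the PMI-only falls of 1.3, 2.2 and 3.6 points as its size. Neither is supported: loss will also occur without PMI, and equal proportions would widen the difference.

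The figures of about 0.7, 1.6 and 3.0 points (5%, 11% and 21% of 14) show scale only. They rest on pilot means taken as true, mean-filling, a true score of 75, and assumed loss rates for which the documents give no basis. They concern the unadjusted PMI contrast, not the adjusted regression or the separate phenotypes. This is a worthwhile, inexpensive improvement rather than a flaw that invalidates the plan.

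**What to change.** - **Consent:** ask each patient to name a relative or carer who may answer if the patient no longer can, and to agree to this. It has to be done before surgery, since permission cannot be obtained from a patient who has lost capacity.
- **Section 5.3, 6-month follow-up:** add that, if the patient is alive but unable to answer, the researcher takes the WHODAS 2.0 from the named contact in the same call and flags it as proxy-reported. Record the reason for every nonresponse.
- **Sections 7.1 to 7.3:** include proxy scores in the primary and disability-free-survival analyses, with a sensitivity analysis without them. Name the imputation variables, including postoperative events.
- **Sections 4.3 and 8.3:** at most one clarifying sentence that they concern entry and that later incapacity does not end follow-up.

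The cost is a line on the consent form, two CRF items (proxy flag and reason for nonresponse) and an ethics amendment. The same researcher makes the same call, so no extra staff are needed. The downside is that proxy answers may differ from self-report; the flag and the sensitivity analysis make the effect of that visible.

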5.4 Withdrawal of individual subjects

Subjects can leave the study at any time for any reason if they wish to do so without any consequences. The investigator can decide to withdraw a subject from the study for urgent medical reasons. After withdrawal, subjects will be treated according standard of care. Subjects can withdraw informed consent for participation in 'deelbiobank' at any time for any reason. Samples and data already used for research, will not be destroyed, but stored in coded form after withdrawal from the 'deelbiobank'.

5.5 Replacement of individual subjects after withdrawal

Subjects who withdraw informed consent will not be replaced by new study participants. The time between signing informed consent and preoperative blood sampling is quite short (on average 30 minutes), hence we assume that it is very unlikely that patients withdraw informed consent before surgery. The collected data up to withdrawal of informed consent is still valid and will therefore be included in the analysis.

5.6 Follow-up of subjects withdrawn from treatment

Not applicable

5.7 Premature termination of the study

Since this is an observational cohort study measuring the difference in pre- and postoperative disability status, premature termination due to futility is not applicable.

6. SAFETY REPORTING

6.1 Temporary halt for reasons of subject safety

In accordance to section 10, subsection 4, of the WMO, the sponsor will suspend the study if there is sufficient ground that continuation of the study will jeopardize subject health or safety. The sponsor will notify the accredited METC without undue delay of a temporary halt including the reason for such an action. The study will be suspended pending a further positive decision by the accredited METC. The investigator will take care that all subjects are kept informed.

6.2 AEs, SAEs and SUSARs

6.2.1 Adverse events (AEs)

Adverse events are defined as any undesirable experience occurring to a subject during the study, related to study procedures including venous blood sampling and noninvasive cardiac imaging. All blood draws for the current study are conducted during venous sampling for routine clinical care, hence potential undesirable experiences related to venous sampling (e.g., pain, bruising), are not to be attributed to the current study.

Adverse events related to noninvasive cardiac imaging, i.e. ECG and TTE include:

- Allergic reaction to the lubricating gel used during the TTE
- Mild skin rash where the electrodes for the ECG were attached

All adverse events reported spontaneously by the subject or observed by the investigator or his staff will be recorded. As these adverse events for both venous blood sampling and noninvasive cardiac imaging are very rare, the risk of participation in this study based on these procedures is low.

